## 5.5 PREMATURE TERMINATION OR SUSPENSION OF STUDY

Study will be terminated if the PI or IRB feels that the rate of adverse events warrants termination or suspension. Study will be suspended if recruiting targets are not met, specifically, if fewer than 70 subjects are recruited at the end of three months, the study will be suspended.

# 6 STUDY AGENT

## 6.1 STUDY AGENT(S) AND CONTROL DESCRIPTION

[figure not shown]
### 6.1.1 ACQUISITION

Shade sensors will be delivered to the study coordinator by the sponsor.

### 6.1.2 APPEARANCE, PACKAGING, AND LABELING

Device:

Figure 6.1.2.1 Shade device

Specifications :

Size: 1.58" diameter, 0.49" height

Weight: 0.48 oz

Battery Life: 4 days (from a full charge); low battery notifications [JC3]

Magnet: Neodymium

Notifications: Light and vibrations

Connectivity: Bluetooth Low Energy

Compatibility: iPhone 5 and above | Android 4.4 and above

Charging: Micro-USB cable included

Recharge time: 1.5 hours

Materials: plastic case

*UV Measurement Sensitivity:*

Wavelength range: 280-400 nm erythemally weighted

Limit of detection: 0.01 UVI. The UV Index is the unit of intensity recommended by the World Health Organization's INTERSUN working group.

[figure not shown]
Maximum UV: 16 UVI

Dosimetry: accuracy and precision 1.5 J/cm^2

## Software

The software consists of firmware in the device, a mobile application, and backend servers to support it. The mobile application has been designed based on user feedback to highlight issues important to people concerned about their exposure to UV light. Specifically it reports the device's estimate of the current UV Index as well as the user's cumulative exposure for the day in units of J/m^2. The software keeps a history of the exposure and allows the user to set a daily limit of UV exposure at which they will receive alerts. The backend manages each user account and stores their historical data to allow retrieval and analysis.

When the device is charged, it indicates connection by momentarily glowing green, then it indicates charging by glowing red. When the device is fully charged, and connected to power, it indicates green. Once powered up, it sends a Bluetooth (BT) signal advertises its presence. In this state it can be paired to a phone using app set to the pairing function. If the device is covered, for example by a jacket, it provides a vibration alert and a mobile phone alert periodically until it is uncovered.

## APPLICATION USER INTERFACE

When the device is first activated and paired with a new mobile device an onboarding protocol is run through (see Attachment 4). The application contains five tabs: dashboard, history, symptoms, chat, and settings.

### *Dashboard:*

The dashboard allows the user to visualize their current exposure, total exposure for the day, as well as an estimate of the time remaining during the day that the user can be exposed to the sun at current intensity levels. From the dashboard the user is also capable of logging their sunscreen (SPF) usage during the day. For a period of time after logging the sunscreen (90 minutes) the reported UV dose is reduced by an amount corresponding to the reported SPF. The history tabs allows the user to visualize their daily UV exposure over the last 12 days.

### *Symptoms:*

From the symptom tab the user is capable of inputting their symptoms with a timestamp that could provide useful feedback to the user on the correlation between symptoms and UV exposure.

### *Chat:*

[figure not shown]

Chat enables users to receive real-time feedback from the company regarding the Shade device and the mobile application usage. This is also a platform for providing feedback to the company, application troubleshooting, or any other questions, comments, or queries the users may have.

#### Settings:

The user can manage general application settings from this tab. For example: it is from this tab that a user can pair their Shade sensor to their mobile phone.

Figure 2-3: Shade Application Key Screenshots

## ALARMS

In use, the device uses two methods to notify the user. (1) shade device vibration and (2) mobile phone alerts.

Notifications are triggered by the following events:

- 1) UV exposure reaches a 20 percent interval of the user's specified daily limit.
- 2) The sensor has been covered making it insensitive to UV.

Additionally, the user can trigger both alert methods by covering the proximity sensor with their finger or the vibration alert by triple tapping the battery indicator on the app's dashboard screen (Figure 2-3, first screen).

Packaging:

The device and user guide are supplied in a white 4.7 x 6.25 x 1.5 inch cardboard box labeled 'Shade.'

Labeling:

User instructions are attached as Appendix 1. The device packaging will be labeled with a sticker indicating 'For Investigational Use Only.'

### 6.1.3 PRODUCT STORAGE AND STABILITY

Store indoors (0-40°C). Product is stable indefinitely.

### 6.1.4 PREPARATION

Prior to use, subject must install a device specific application on their mobile phone. The Study Coordinator or a sponsor representative will assist them in this process. As part of the use of this application the user enters an email address. Subjects will *not* enter their own email address and will instead enter a non-functional study email address assigned by the study coordinator. See data management sections for details.

### 6.1.5 DOSING AND ADMINISTRATION

N/A

### 6.1.6 ROUTE OF ADMINISTRATION

N/A

### 6.1.7 STARTING DOSE AND DOSE ESCALATION SCHEDULE

N/A

### 6.1.8 DOSE ADJUSTMENTS/MODIFICATIONS/DELAYS

N/A

### 6.1.9 DURATION OF THERAPY

9-12 months

### 6.1.10 TRACKING OF DOSE

N/A

### 6.1.11 DEVICE SPECIFIC CONSIDERATIONS

The device is worn externally, magnetically affixed to the subject's clothing. The device vibrates to communicate to

subjects when they have accumulated UV dosage and when the device is covered. The mobile application provides similar alerts with accompanying explanatory text.

## **6.2 STUDY AGENT ACCOUNTABILITY PROCEDURES**

Product will be delivered to the study coordinator by the sponsor. The delivery slip will include a receipt with a list of device serial numbers. The study coordinator will acknowledge receipt and return the signed packaging invoice to sponsor. Supplies should be kept in a secure area.

The study coordinator will maintain a device disposition table with the columns: S/N, Subject ID, Date dispensed, Dispensed by (name of study personnel), Date returned, Returned to (name of study personnel), Comments (e.g. working/broken/lost). The device disposition table is considered confidential and should be viewed only by the study coordinator and study monitors, physicians must remain blinded to the device disposition table.

# **7 STUDY PROCEDURES AND SCHEDULE**

## **7.1 STUDY PROCEDURES/EVALUATIONS**

### **7.1.1 STUDY SPECIFIC PROCEDURES**

Cyclobutane pyrimidine dimers (CPD) levels will be measured by ELISA from exposed (cheek) and unexposed (buccal mucosa) skin scrapings. The area from which the cutaneous scraping is collected will be cleaned with an alcohol swab. Using a 15 blade, the epithelial cell will be lightly scraped on the cutaneous cheek and the buccal mucosa. The skin cells will be placed in an eppendorf tube and put on ice. These eppendorf tubes will be transported to a research lab where ELISA testing will be performed by a technician. For each patient, the CPD level from exposed skin will be normalized to the sun protected CPD level measured from unexposed skin. A physician will compare the normalized CPD level of control versus study participants at each timepoint and their average CPD change over time.

**Clinical counting of AKs:** The physician will identify actinic keratosis based on a visual and textural examination. If the actinic keratosis is large and continuous it will be counted as one actinic keratosis. The actinic keratosis will then be circled and photographed. The photograph will be available in the patient medical record but will not be copied to the CRF. The areas that are identified during the visit will be treated. Photos will be taken at each visit. At subsequent visits, the previous visits, photos will be reevaluated to prevent double counting. All lesions suspected of malignancy will be biopsied and subject to histological examination. These lesions will be reclassified according to histology diagnosis if necessary.

#### **7.1.2 STANDARD OF CARE STUDY PROCEDURES**

##### **Skin Check**

A standard skin examination will be performed by a dermatologist. The scalp, face, mucous membranes, chest, back abdomen, arms, legs, genitalia, digits will be examined at the first and last visit (V1 and V3). A focused examination of the scalp, face, hands and any other pertinent areas will be performed at the second visit (V2).

##### **Treatment of actinic keratosis**

When an actinic keratosis (AK) is identified, the area will be identified with a marking pen. The areas will be photographed and the photos attached to the patient's chart. The areas will then be treated with a destructive modality. The most common technique that will be employed is cryotherapy with liquid nitrogen or curettage of the actinic keratosis. Any AK that is suspicious or resistant to treatment will be biopsied via shave technique. Shave technique is described as the removal of entire lesion using a dermablade with 1-2 mm margins.

##### **Ultraviolet Exposure Counseling**

*The dermatologist will make the following recommendations to each patient having a skin cancer screening.*

- Always use a sunscreen product with a minimum SPF of 30 when going outdoors, even on a cloudy day.
- Avoid exposure to the sun during the peak hours between 10 AM and 4 PM and to stay in the shade when possible.
- Wear protective eyewear during peak sun hours.
- If sunscreen is not available, always wear protective clothing, such as long-sleeved shirts and pants, wide-brimmed hats, and sunglasses with UV protection.
- Routinely examine skin at least once a month for any visible changes or changing lesions.
- Avoid the use of tanning products or tanning beds.
- See your dermatologist yearly for a professional skin exam

## 7.2 LABORATORY PROCEDURES/EVALUATIONS

### 7.2.1 CLINICAL LABORATORY EVALUATIONS

#### 7.2.1.1 CPD Assay

The CPD Assay will employ a commercial ELISA based test. It will be carried out following a detailed written protocol developed by the investigating laboratory based on the manufacturer's published procedure. The validation of this procedure will be presented by the laboratory manager and this validation along with the protocol will be reviewed by the PI and the sponsor. Once implemented, the procedure will be carried out on clinical samples with attention to good laboratory practice.

### 7.2.2 OTHER ASSAYS OR PROCEDURES

N/A

### 7.2.3 SPECIMEN PREPARATION, HANDLING, AND STORAGE

Skin scraping will be collected as described in 7.1.1 Study specific procedures.

The tubes containing the samples and any secondary containers will be labeled by: ###-S and visit number

- study subject number ###
- site S which is one of B (buccal mucosa) or S (skin)
- visit number # = 1,2,3

The specimens will be stored in liquid nitrogen or at -80°C in the clinic in a labeled separate container for materials for this study. Samples will remain in this container until collected by laboratory staff.

### 7.2.4 SPECIMEN SHIPMENT

Skin scrapings will be transferred to the New York Presbyterian Laboratory at [name]. Staff will carry the samples to the clinical lab in an insulated container immersed in liquid nitrogen and then samples will be stored in liquid nitrogen or at -80°C prior to being processed by the laboratory technical staff.

## 7.3 STUDY SCHEDULE

### 7.3.1 SCREENING

A pre-screening/recruiting phone call will occur before scheduling the screening visit. This call will establish the subjects probable eligibility for the study.

At the screening visit the study coordinator will assess eligibility by checking for inclusion and exclusion criteria and entering these results in the CRF.

Following inclusion/exclusion questions, the study coordinator will obtain informed consent from the subject. Only subjects who satisfy all screening criteria and provide consent will be enrolled in the study.

### 7.3.2 ENROLLMENT/BASELINE

During the enrollment visit the physician will complete a medical history including an assessment of Fitzpatrick skin type. The enrollment visit will include standard of care counseling on the importance of UV avoidance. For transplant recipients, condition appropriate information will be included.

Ultraviolet Exposure Counseling: as described in 7.1.2 Standard of Care Study Procedures

The enrollment visit will include the skin check described in 7.1.2 Standard of Care Study Procedures.

Skin Check: as described in 7.1.2 Standard of Care Study Procedures

Treatment of Actinic Keratoses as described in 7.1.2 Standard of Care Study Procedures.

At the conclusion of the enrollment visit the study coordinator will discuss with enrolling physician for determination of Fitzpatrick skin type. The coordinator will then assign the subject to treatment or control groups following the procedure in section [10.6.1](#). The subject's assignment will be noted on the randomization table to be kept confidential to the coordinator and study monitors.

The coordinator will meet with the subject in a separate room to schedule the first follow up visit. If the subject is in the treatment arm, in this meeting the subject will be given the box with the Shade sensor. The coordinator or a sponsor representative will observe and support the subject in the process of opening the box and installing the application on their phone. At this time the coordinator will assign a study email address to the subject and enter that address in the randomization table and an electronic table along with the subject's actual email address.

### 7.3.3 FOLLOW-UP

A focused examination of the scalp, face, hands and any other pertinent areas will be performed at the follow up visit(s). AKs will be identified and photographed. Any other suspicious lesions will be biopsied as described as above. AKs will be treated as previously described.

The study coordinator will maintain the schedule of follow up visits and will contact subjects via phone or email. In the event that a subject in the treatment arm is having difficulty achieving compliance, the study coordinator will be available for counseling, training, to provide replacement of broken or lost devices, and encouragement. Calls will be logged in the study binder.

### 7.3.4 FINAL STUDY VISIT

For the final visit, a standard skin examination will be performed by a dermatologist. The scalp, face, mucous membranes, chest, back abdomen, arms, legs, genitalia, digits will be examined. Any AKs will be identified, photographed and treated as previously described. Any suspicious lesions will be biopsied. If the patient is in the study arm, the device will be collected by the study coordinator at this visit.

### 7.3.5 EARLY TERMINATION VISIT

Subjects who withdraw consent or otherwise voluntarily leave the study will be offered the opportunity to participate in the next visit scheduled for the study.

Subjects who are dropped from the study for any reason will be contacted by phone to explain the reason they have been dropped from the study. An early termination visit is not required.

Subjects who terminate early will be asked to return their Shade device and will be given the same offer to obtain a new device of their own as subjects who complete the study.

The study coordinator will fill out a study termination form for all subjects including those who leave early.

### 7.3.7 SCHEDULE OF EVENTS TABLE

Procedures	Prior to enrollment	Enrollment	Visit 1	Before visit 2	Visit 2	Before visit 3	Visit 3	AE Visit
Screening call	X							
Screening questions		X						
Informed consent		X						
Medical history		X						
Patient survey			X		X		X	
Dermatology Visit			X		X		X	
UV counseling			X		X		X	
Full Skin Check			X		X		X	
Focused Skin Check			X		X		X	
Collect skin scraping (WCM only)			X		X		X	
Randomization			X					
Compliance engagement				X		X		
Return study materials							X	
Condition driven medical exam								X

Screening call:

Screening questions: These are listed in the CRF

Informed consent: As approved by IRB

Medical history: Key questions listed in CRF

Patient survey:

Dermatology visit:

Collect skin scraping:

Randomization:

Compliance engagement:

Return study materials: See section 7.9

### 7.4 JUSTIFICATION FOR SENSITIVE PROCEDURES

There are no sensitive procedures in this study.

### 7.5 CONCOMITANT MEDICATIONS, TREATMENTS, AND PROCEDURES

Concomitant medications, treatments and procedures will be recorded in the CRF.

#### 7.5.1 PRECAUTIONARY MEDICATIONS, TREATMENTS, AND PROCEDURES

None

## **7.6 PROHIBITED MEDICATIONS, TREATMENTS, AND PROCEDURES**

The use of topical and oral medications prescribed as field treatment for actinic damage (i.e., imiquimod, acitretin, etc.) would be prohibited during this study. Targeted topical treatment of biopsy-proven non melanoma skin cancer (e.g. imiquimod) would be allowed at the provider's discretion. Any treatment of actinic keratoses or any biopsies of suspected malignancies by an outside dermatologist would be prohibited during the study

## **7.7 PROPHYLACTIC MEDICATIONS, TREATMENTS, AND PROCEDURES**

None

## **7.8 RESCUE MEDICATIONS, TREATMENTS, AND PROCEDURES**

None

## **7.9 PARTICIPANT ACCESS TO STUDY AGENT AT STUDY CLOSURE**

At the conclusion of the study subjects in the treatment arm will

1. Return the Shade device used in the study.
2. Receive a printout of their UV history from the study coordinator.
3. Delete the shade mobile application from their phone.

All subjects will

4. Choose between receiving the final study compensation at the visit or a coupon usable to purchase a new sensor. The coordinator will explain that if they use the coupon, Shade will know that they participated in the study. But Shade will not know their subject ID and will therefore not be able to connect their identity to medical records provided in the study.

# **8 ASSESSMENT OF SAFETY**

## **8.1 SPECIFICATION OF SAFETY PARAMETERS**

The primary safety endpoint is the number of adverse events related or possibly related to the device or sun exposure experienced within the study period. To test this hypothesis the number of adverse events related or possibly related to the device or sun exposure experienced by the treatment group should not be significantly greater than the number of adverse events related or possibly related to the device or sun exposure experienced by the control group throughout the duration of the study. Adverse events will be categorized by type, duration, severity, relationship to the study device and need for treatment.

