### **8.1.1 DEFINITION OF ADVERSE EVENTS (AE)**

An AE is any untoward medical occurrence in a patient or clinical investigation subject administered a pharmaceutical product and that does not necessarily have a causal relationship with this treatment. An AE can therefore be any unfavorable and unintended sign (including an abnormal laboratory finding), symptom, or disease temporally associated with the use of a medicinal (investigational) product, whether or not related to the medicinal (investigational) product (see the ICH guidance for Clinical Safety Data Management: Definitions and Standards for Expedited Reporting).

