#### Relatedness

The potential event relationship to the study intervention and/or participation is assessed by the site investigator. A comprehensive scale in common use to categorize an event is:

- *Definitely Related*: The adverse event is clearly related to the investigational agent/procedure – i.e. an event that follows a reasonable temporal sequence from administration of the study intervention, follows a known or expected response pattern to the suspected intervention, that is confirmed by improvement on stopping and reappearance of the event on repeated exposure and that could not be reasonably explained by the known characteristics of the subject's clinical state.
- *Possibly Related*: An adverse event that follows a reasonable temporal sequence from administration of the study intervention follows a known or expected response pattern to the suspected intervention, but that could readily have been produced by a number of other factors.
- *Not Related*: The adverse event is clearly not related to the investigational agent/procedure. - i.e. another cause of the event is most plausible; and/or a clinically plausible temporal sequence is inconsistent with the onset of the event and the study intervention and/or a causal relationship is considered biologically implausible.

Mild sunburns, not requiring medical treatment, are expected to be over reported in the treatment group because of their constant communication with the application. These will not be considered AE's for the purposes of the safety endpoint.

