### ***10.4 DESCRIPTION OF STATISTICAL METHODS***

Actinic keratosis (AK) is a frequent pre-cancerous skin lesion caused by damage from ultraviolet exposure. Without treatment, 1-2% of these lesions evolve into squamous cell carcinoma (SCC). Therefore, the number of AKs reflects the effect of UV exposure and the risk for SCC. Transplant patients are at high risk of skin cancer because of their immunosuppressive medications required to prevent organ rejection. Morbidity/mortality of SCC in this patient population can be as high as 25%.

The primary outcome of this trial will be a statistically significant reduction by at least 25% in the cumulative number of newly developed AK lesions between the control and the study group.

AK lesions on sun exposed skin areas (scalp, face, hands) will be counted and reported by dermatologists at enrollment and at each subsequent visit. AKs are defined as keratotic macule(s) or papule(s) on an erythematous base by dermatological examination. In addition to the enrollment visit, this study will include a follow up dermatological visit after the summer. For each patient, the number of newly occurred AKs will correspond to the cumulative AK counts during the study period. To insure that only new occurrences of AK lesions after V1 will be counted, data from subsequent study visits will include the location of AK lesions and pictures of the lesions.

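### As worded, the primary safety count can be biased in either direction: adverse-event reporting is not equalised between arms, and UV-caused lesions are not expressly excluded

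*Combined protocol and SAP*

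**What the plan says.** Section 8.1 defines the primary safety endpoint as the "number of adverse events related or possibly related to the device or sun exposure experienced within the study period". The decision rule is that the study-arm number "should not be significantly greater than the number of adverse events related or possibly related to the device or sun exposure experienced by the control" arm. Events are also to be categorised by, among other things, type, severity and relationship to the device.

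Section 8.1.1 defines an adverse event broadly, as "any unfavorable and unintended sign (including an abnormal laboratory finding), symptom, or disease temporally associated with the use" of the product, whether or not the product caused it. Section 8.2.3 sorts events into expected and unexpected but drops neither kind. Its Relatedness text makes one exclusion from the safety endpoint, mild sunburns needing no medical treatment, on the ground that they "are expected to be over reported in the treatment group because of their constant communication with the application".

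On how events come to light, 8.3 starts from events that subjects report. The schedule in 7.3.7 has a patient survey at every visit and an event-driven AE visit, but no adverse-event question. The app's symptoms tab means "the user is capable of inputting their symptoms with a timestamp", and its chat tab connects users to the company. Section 7.3.3 adds: "In the event that a subject in the treatment arm is having difficulty achieving compliance, the study coordinator will be available for counseling". Controls have no sensor (2.2).

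On the lesions, 10.4 states: "Actinic keratosis (AK) is a frequent pre-cancerous skin lesion caused by damage from ultraviolet exposure". New AKs are endpoint 1, and endpoints 2-4 cover AKs at the final visit, SCCs, and BCCs with SCCs.

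**The concern.** There are two separate problems, both about what enters the count rather than about how it is tested.

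The first is unequal ascertainment. The stated reason for excluding mild sunburn is that study-arm subjects are in constant contact with the app. That reason is not specific to sunburn. It applies to any minor event that a person might or might not mention. The plan recognises the mechanism, deals with one event type, and leaves the rest dependent on spontaneous reporting in an open-label comparison where one arm has more prompts to report.

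The second is an open boundary with efficacy. An event related to sun exposure, under a broad definition of adverse event, literally takes in a new AK, SCC or BCC. No sentence excludes them. If some staff enter them and others do not, the safety count becomes partly an efficacy count, and a device that reduces AKs would offset other events.

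Section 3 says the trial is to demonstrate safety as well as effectiveness and to support the indications for use. A count that can move for reasons unrelated to harm is weak support for that.

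**Working it through.** The documents give no adverse-event rate, margin or power for the safety endpoint, so there is no stated figure to reproduce. The calculations below show the size of each mechanism under stated assumptions.

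**Inputs from the documents.** 120 subjects randomised 1:1, so 60 per arm (4.1). Two-tailed 0.05 (10.4.1), which is 0.025 in the direction of excess harm. A 25% reduction in AKs as the target effect (10.4).

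**Assumptions.** Poisson counts; a control rate *a* of counted events per subject, other than AKs, of 0.05, 0.3 or 0.5; a capture ratio *k* (study arm to control) of 1.25, 1.5 or 2; and an exact conditional test, since no safety test is specified.

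**Unequal capture, no true difference, AKs not counted.** Control events are Poisson with mean 60*a*, and study-arm events are Poisson with mean 60*ak*. Given the total T, study-arm events are binomial with T trials and probability *k*/(1+*k*), which is 0.556, 0.600 or 0.667. The test declares excess harm at *x* study-arm events when P(Bin(T, ½) ≥ *x*) ≤ 0.025. Averaging over T, which is Poisson with mean 60*a*(1+*k*), gives:

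| Rate per control (expected control events) | k = 1.25 | k = 1.5 | k = 2 |
|---|---|---|---|
| 0.05 (60 × 0.05 = 3) | 2% | 3% | 9% |
| 0.3 (60 × 0.3 = 18) | 8% | 22% | 65% |
| 0.5 (60 × 0.5 = 30) | 12% | 37% | 87% |

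With equal capture the rate is at most 2.5%. A t-test on subject counts gives a similar row at 0.5 events per control: 14%, 41% and 89%.

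**Lesions counted, true doubling of other events.** Take 0.5 other events per control, doubled in the study arm, and 25% fewer AKs with the device.
- 2 AKs per control (assumed): control 60 × (0.5 + 2) = 150; study arm 60 × (1.0 + 0.75 × 2) = 150.
- 5 AKs per control (assumed): control 60 × (0.5 + 5) = 330; study arm 60 × (1.0 + 0.75 × 5) = 285.

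The doubling is flagged in about 87% of trials if AKs are left out, in about 2% with 2 AKs per control, and in under 0.1% with 5.

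**The two mechanisms together.** They pull in opposite directions. With 0.5 other events per control, *k* = 2, no true harm and 2 AKs per control counted, the false-flag rate falls from 87% to about 36% if the device does not change AKs, and to about 2% if it cuts them by 25%. The net direction cannot be known in advance.

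**The case against.** A reader might infer that the safety count includes the efficacy lesions. The documents do not say so, and their operating text leans the other way. Under 8.4.1 a treating physician judges whether an event reaches AE status, and each AE then goes to the PIs and the IRB within 24 hours, which would be an odd route for every AK. Section 8.6 lists AEs and AK occurrence as separate items. Section 10.4.10 gives AK, NMSC and AE separate columns. This stands: the lesion problem is a missing exclusion, not a stated inclusion.

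A reader might also infer that app and chat entries feed the AE count directly. Section 10.4.10 takes that count from the CRF, and the CRF sources in section 11 name neither channel. Nor does 7.3.7 restrict compliance engagement to one arm. This stands too. What remains is indirect: logging a symptom or talking to the coordinator about the device can prompt a report, and 8.3 then leads to an assessment. The physician is kept blind and staff record all visits and hospitalisations (8.6), which protects the judgement of events that reach the clinic and the capture of serious ones. It does not equalise which minor events get mentioned.

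Third, 0.3 to 0.5 related events per control may be high for a clip-on sensor in a study described as minimal risk. At 0.05 the false-flag rate is only 2% to 9%. That is fair, and the low row belongs in the table.

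Finally, 8.1 categorises events by relationship to the device, so device-related harm would stay visible even if lesions were counted, and a false flag requires a test when 10.4.4 plans no safety analyses. The first point limits the masking problem to the headline count. The second is a separate inconsistency with 8.1, and adding a test would not repair a count collected unequally.

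**Conclusion.** The concern holds in a limited form. As worded, the primary safety count can be biased upward by study-arm reporting that the protocol itself anticipates but corrects for one event type. It can be biased downward if UV-caused lesions are entered as adverse events, which the text neither states nor rules out. The stronger conclusion, that the endpoint cannot compare harm between arms, is not supported. Serious events should be captured in both arms, and relationship to the device is recorded.

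The size is uncertain. It ranges from negligible (about 2% false flags at 0.05 events per control and 1.25-fold capture) to severe (about 87% at 0.5 and twofold capture). These figures assume 60 per arm, Poisson counts, no true difference, AKs not counted and a one-sided 0.025 test. Neither the event rate nor the capture ratio is in the documents. The CRF is not among them either; if it already carries a common AE question, the first problem shrinks to one of documentation. The change is cheap and should be made.

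**What to change.** In 8.1 and 8.2.3:

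1. Base the between-arm safety count on adverse events elicited with one identical question in both arms at visits 2 and 3. List events that arrive only through the app, chat or compliance calls separately and in full, so that no device harm is lost from view. Reporting under 8.4 is unchanged for every event from any channel.
2. State that AKs, SCCs and BCCs found at study examinations are analysed as endpoints 1-4 and are not in the safety count. Report device-related events separately from sun-exposure events.
3. Keep the mild-sunburn exclusion in the main count. Mild sunburn elicited by the common question may be tabulated on its own.

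The cost is a few sentences and one question at visits where subjects already complete a survey. The downside is that minor events between visits may be forgotten, and study-arm subjects' app logs may help their recall, so the imbalance is reduced rather than removed.
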